Baseline and follow-up surveys will be identical (with few exceptions i.e., age, sex, race / ethnicity) including: *Demographic and CSDH characteristics*¹⁷²; and *PhenX consensus measures*, including the Addiction Severity Index¹⁷⁴,fatal and non-fatal overdose episodes^{177,178}, intersectional opioid-related stigma¹⁸⁰, Everyday Discrimination Scale,¹⁸¹ social network characteristics¹⁸² and Medical Outcomes Study Social Support Survey¹⁸³, harm reduction and social services use¹⁸⁴, MOUD and Buprenorphine Treatment and Adherence, and Non-Study Medical and Other Services (NMOS) (See *Table 2*).

During follow-up, the *REDCap Survey* will capture Timeline Follow Back interview¹⁷³ and the domains of the Technology Acceptance Model¹⁸⁷ (see *Figure 2*): *perceived usefulness, perceived ease of use, attitudes, behavioral intentions, and intervention usage.* In addition, data for each of these components will be derived from: the texting software (e.g., rate of participant responses to software-initiated text queries, number of participant-initiated requests for physician telephone assistance^{53,129,188,189}), and through *PRC communication logs* and *qualitative interviews* to inform fidelity, implementation, and contextualize intervention efficacy, enhancing RE-AIM and CFIR frameworks.

		Quantitative Domains and Variables
12 months)	Sociocultural & demographic determinants of health	 Demographic characteristics (e.g., age, gender, race/ethnicity) Socioeconomic conditions related to education, employment/financial status, family/social relationships, criminal justice involvement (Criminal and Legal Activities Form), family/social relationships, and housing status (Housing Instability Scale) Structural determinants of health (Social Vulnerability Index) Individual social determinants of health (Disparate Health Care Quality) Access to health services (modified National Health Interview Survey) Access to technology / use for health needs (Health Information National Trends Survey) Intersectional stigma/discrimination of OUD and other social statuses e.g., race, ethnicity, gender, sexual identity, etc. (Brief Opioid Stigma Scale; Everyday Discrimination Scale)¹ Social network composition, size, social supports based on instrumental, informational, emotional support domains (Medical Outcomes Study Social Support Survey)

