Baseline & Follow-up (3, 6, 12 n	Substance use & Sexual risk behavior (outcomes, exposures & confounders)	 Substance use risk, including type, frequency, route, duration, and locations of illicit substance use (Addiction Severity Index) Increase, decrease, and persistent use during follow-up (Timeline Follow-Back) Syringe sharing, polysubstance use, non-fatal overdose (Risk Behavior Survey) Medical, behavioral health, harm reduction, and substance use treatment utilization (Timeline Follow-Back, Non-Medical and Other Resources) Cognitive Function-Abilities, Depression, Pain Intensity, Physical Function, Sleep Disturbance, and Ability to Participate in Social Roles and Activities [Patient-Reported Outcomes Measurement Information System (PROMIS) - Preference (PROPr)] Satisfaction with telemedicine based opioid treatment (Treatment Satisfaction Survey) and patient centered care (Patient-centered care climate questionnaire) Salivary drug screen (baseline only) Sexual risk (e.g., type/frequency unprotected sex, # of partners; HIV risk screening tool)
Ва	Clinical & Social services use (per self-report and audits of the EPIC EHR "care everywhere" tool)	Buprenorphine treatment linkage and adherence (modified PhenX Treatment for Substance Use, self-reported medication dose logs) Harm reduction and social service utilization (NMOS) Satisfaction with Al-driven text messaging tool, NYC DOH pamphlets (i.e., control arm) and PRC support (Participant feedback survey) PRC services use and patient-centeredness (OPTION scale for patient involvement)
	Psychological & Physical factors	 Depression (e.g., Hamilton Depression scale) and anxiety (Hamilton Anxiety Scale) Quality of life/self-rated health (SF-12) Pain: indicate pain on diagram; rate pain at its worst; medications receiving for pain; % relief from medications; how pain has interfered with life activities⁸

Subject Payment

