Participants randomized to TAU will receive similar payments at the same time points as participants in the intervention arm-1 and arm-2 groups. At the completion of each of the follow-up sessions all participants are compensated for their time.

Proposed Analyses

Aim 1 is a 3-year RCT involving community and ED-enrolled Black / Latinx PWUO who will be screened and enrolled (N=252) **Primary outcomes** will be based on remote and/or in-person follow-up assessments at 3-, 6-, and 12-months and consists of self-reported linkage to primary care-based OUD services (i.e., time to initial receipt of buprenorphine in primary care). **Secondary outcomes** include durability of treatment effect at 52 weeks (e.g., continuous retention in OBOT with buprenorphine), receipt of social services, and longitudinal engagement with the proposed intervention (up to 26 weeks).

Our primary hypothesis is that the rate of linkage to OBOT, i.e., time to first buprenorphine prescription, will be highest among PWUO participants randomized to texting + PRC, followed by those randomized to texting only, then to TAU. To assess this hypothesis, we will utilize Cox proportional hazards (PH) regression to investigate differences in time to service linkage (in days) by intervention group. Cox PH regression is a method for investigating the effect of several variables on the time to a specified event¹⁷⁰. Cumulative hazards functions for the intervention groups will be examined using Nelson-Aalen plots and use the supremum test which uses martingale residuals to check the proportional hazards assumption. If the assumption is violated such that there is no difference in the direction of the association but there is variation in the magnitude of the association, i.e., the hazards ratio (HR) changes over time, then the coefficient that we estimate for that covariate is akin to an 'average effect' over timepoints that are observed in a dataset and the Cox PH model will perform moderately. If the hazards cross, i.e., a change in the direction of the association, the Cox PH model will perform poorly, and we will extend the Cox model to allow for nonproportional hazards using time dependent covariates. Intervention group as assigned will be the sole explanatory variable in the models (see **Methodological Considerations and Alternatives**).

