Secondary and exploratory analysis will rely on data collected at 3-, 6-, and 12-month follow-up surveys that will permit analysis of secondary outcomes of: (1) durability of treatment effect at 52 weeks (e.g., continuous retention in OBOT with buprenorphine); (2) engagement with social services; and (3) longitudinal engagement with the proposed intervention (up to 26 weeks). For these analyses, we will use generalized linear mixed effects regression to model binary outcomes indicating longitudinal engagement in 26-week treatment (yes/no) and continuous retention in buprenorphine treatment at 3-, 6-, and 12-months (yes/no) with no more than a 28-day gap in receiving an active buprenorphine prescription over each period. These models will include a participant-specific random intercept to account for the repeated-measures structure of the data.

Methodological Considerations and Alternatives: To assess whether randomization was successful, we will compare the distribution of demographic characteristics, PhenX consensus measures, medical/psychiatric history, technology use patterns, and risk behavior variables (see *Data Collection*) by intervention arm. Variables contributing to baseline imbalance will need to be included as adjustment variables in regression models.

Missing Data and Sensitivity Analysis will rely on ensuring that the model assumption of non-informative study dropout or missing at random is reasonable and avoid potential bias, we will compare dropout rates between intervention groups as well as other measured variables, e.g., medical/psychiatric history, technology use patterns, and risk behavior variables. If there is empirical evidence of nonrandom dropout, we will model the dropout event using available factors to identify and estimate their influence. To meet missing at random model assumption, variables that predict dropout will be included as auxiliary variables via multiple imputation.

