- b. Harm reduction content, sent 2x/week, includes opioid overdose prevention training, instructions linking with primary care to receive opioid overdose education, naloxone, and instructions to access city-wide harm reduction sites offering sterile syringes, naloxone, and supervised injection services if desired:
- c. Motivational enhancement content, sent 3x/week, encourage uptake of OBOT services by evoking self-motivational replies and commitments to text prompts, building motivation for planned uptake, establishing a plan for uptake, adopting treatment adherence and maintenance strategies after confirming uptake per text queries, and applying coping strategies for high-risk situations that may precipitate the risk of illicit use;

- d. Medical Management content tailored to OBOT after confirming entry in treatment using 2x/week text "check-ins". Text categories will consist of: (1) Support during induction and stabilization to buprenorphine that targets buprenorphine adherence and selfmanagement with a once daily text at 9:00 am assessing for withdrawal symptoms. For a "Yes" response to withdrawal symptoms, participants will receive: (a) instructions on buprenorphine and/or comfort medication administration; (b) query for continued opioid use; and c) repeat queries at 12:00pm and 6:00pm for cravings and withdrawal symptoms. If participants report "Yes" to opioid use, they will be informed of the risk of overdose and may request a physician phone call during regular clinic hours (i.e., patient-provider communication); (2) Appointment adherence "tips" (e.g., setting written/mobile phone calendar reminders) that enhance self-management sent 1x/week; (3) Supportive content comprise alternating messages between medication adherence (e.g., buprenorphine), reinforcement of reducing harmful substance use, or 12-step meeting and counseling participation (i.e., hotlines, meeting sites / schedules, free online resources): (4) Educational content that enhance self-management with medication dosing, side-effects, overdose prevention, and online public-facing resources:
- e. Instant help allows participants to query the texting software and receive personalized motivational enhancement, educational, or clinic/social services contact details via menu items and open-ended queries captured by natural language processing to enhance patient-physician communication.

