Patient Cohort. In this study we will use the FDA definition of serious adverse events (SAEs). Both adverse events (AEs) and SAEs will be systematically assessed at each clinic visit for the patientparticipants. We do not anticipate SAEs are AEs related to the use of text messaging which is our intervention. Any SAE, whether or not related to study intervention, will be reported to the IRB and NIDA. The initial SAE report will be followed by submission of a completed SAE report to both institutions. In the event that a patient either withdraws from the study or the investigator decides to discontinue a patient due to SAE, the patient will be monitored by the investigator via ongoing status assessment until 1) a resolution is reached, for example the problem requiring hospitalization has resolved or stabilized with no further changes expected, 2) the SAE is determined to be clearly unrelated to the study intervention, or 3) the SAE results in death. SAEs would include hospitalization (for example as the result of an opioid overdose, which is not uncommon among high-risk OUD patients) or opiate overdose resulting in death. The study team will conduct, at a minimum, an annual Data Safety Board meeting to review all SAEs. All PI's will attend this meeting. If more than 2 SAEs occur in any year, meetings of the board will be increased in frequency. All observed SAEs (again, regardless of relation to the study intervention) will be periodically reported to NIDA. A summary of the SAEs that occurred during the previous year will be included in the annual progress report to NIDA. The MPIs will be responsible for monitoring and recording both AEs and SAEs.

Provider and administrator study participants providing in-depth interview data. We do not anticipate any AEs or SAEs for the clinician and administrator participants undergoing virtual indepth interviews (Aim 2). For this sample we will also adopt the FDA definition of an SAE. AEs and SAEs for the provider and administrator sample will be handled exactly as specified for the PWUO participant cohort.

Standard AE definitions will include the following:

Adverse event: Any untoward or unfavorable medical occurrence in a human subject, including any abnormal sign (for example, abnormal physical exam or laboratory finding),

symptom, or disease temporally associated with the subject's participation in the research, whether or not considered related to the subject's participation in the research.

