The following will be included in the DSM report: 1) brief description of protocol, 2) baseline socio-demographic characteristics, 3) retention and disposition of study participants, 4) quality assurance issues, 5) AEs, 6) SAEs, 7) efficacy, 8) suggested and actual protocol changes

Interim Data Analysis Plans

Interim analyses will be performed to evaluate safety. At each DSMB meeting, all SAEs will be evaluated and compared between study groups. If SAEs differ between groups in a manner determined to be related to study procedures, the study will be paused. Decisions to pause the study will be made by the independent DSMB.

In addition to consistent monitoring by members of the research team for adverse events, quarterly interim analyses of the survey data, quality control checks, and study activities will also be performed to ensure that all participant data are protected and there are no adverse events or harm to participants. During this review, validity and integrity of the data will also be monitored.

References

- [name] JD, Nunes Jr EV, Novo P, et al. Comparative effectiveness of extended-release naltrexone versus buprenorphine-naloxone for opioid relapse prevention (X: BOT): a multicentre, open-label, randomised controlled trial. *Lancet*. 2018;391(10118):309-318.

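### Overdose is asked about at every survey but never compared between arms, and the planned SAE comparison may not show how often it occurs

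*Combined protocol and SAP*

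**What the plan says.** **Collection.** Data Gathered lists "fatal and non-fatal overdose episodes" among the survey measures and adds: "Baseline and follow-up surveys will be identical (with few exceptions i.e., age, sex, race / ethnicity". Table 2, which covers baseline and the 3-, 6- and 12-month follow-ups, includes "Syringe sharing, polysubstance use, non-fatal overdose (Risk Behavior Survey" in a domain that it labels as holding outcomes as well as exposures and confounders.

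**Analysis.** Under Proposed Analyses, the primary Aim 1 model examines "differences in time to service linkage (in days) by intervention group". The secondary outcomes begin "1) durability of treatment effect at 52 weeks (e.g., continuous retention in OBOT with buprenorphine); (2) engagement with social services" and end with engagement with the intervention. Data Entry & Analysis repeats this set in substance. The RE-AIM effectiveness row of Table 3 does not list overdose either. Risk-behavior variables appear only in baseline-balance checks, in dropout checks, and as help in interpreting a null result.

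**Safety.** Interim Data Analysis Plans says: "At each DSMB meeting, all SAEs will be evaluated and compared between study groups". AEs are an item of the DSM report, with no comparison by arm stated. The same section plans quarterly looks at the survey data for harm, but names neither overdose nor a contrast between arms.

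**What counts as serious.** Collection and Reporting of SAEs and AEs gives, as examples, "hospitalization (for example as the result of an opioid overdose, which is not uncommon among high-risk OUD patients") and fatal overdose. The SAE definition that follows also covers life-threatening events, and events that in medical judgement may need intervention to prevent a listed outcome.

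**Difference between arms.** The harm-reduction texts, sent twice a week, include "opioid overdose prevention training, instructions linking with primary care to receive opioid overdose education, naloxone". Only arms 1 and 2 are entered in the texting software. TAU receives verbal instructions and pamphlets.

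**The concern.** Overdose death is the stated reason for the trial, and the protocol itself expects overdose admissions in this population. A reader of the final report will want to know whether overdoses differed by arm. As planned, the only by-arm information would come from SAEs, and an SAE count mixes two things: how often people overdose, and what happens after they do.

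The intervention may act on the second. Someone prompted to obtain naloxone may be more likely to have an overdose reversed without admission. If such an event is not recorded as an SAE, the texting arms can show fewer overdose SAEs with no fall in overdoses, or the same number despite a rise. The DSMB would see the same table, because its between-group safety review is framed in terms of SAEs.

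**Working it through.** The plan states no overdose rate, SAE rate or safety power, so there is no figure to reproduce. What follows is a check of the text and then an illustration on assumed inputs.

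**1. Is there a by-arm overdose analysis?** The primary, secondary, Data Entry & Analysis and RE-AIM texts were compared with Table 2. Overdose is collected and is not an outcome in any of them.

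**2. Is a reversed, non-admitted overdose an SAE?** The two parts of the safety text give different signals.
- Narrow reading: the examples name hospitalized and fatal overdose, and the AE grading says a severe event becomes an SAE if hospitalization is required. A reversed overdose without admission would be an AE.
- Broad reading: the life-threatening and medical-intervention criteria could both include it.

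The documents do not say which applies.

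**3. Effect on the SAE count.** Let *q* be the 12-month risk of overdose (one per affected person) and *s* the share ending in admission or death. With 84 per arm (from the protocol; *q* and *s* are assumptions):

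- Narrow reading: expected overdose SAEs = 84 × *q* × *s*
- Broad reading with complete reporting: expected overdose SAEs = 84 × *q*

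At equal *q*, the narrow-reading ratio of texting arm to TAU is *s*(text) / *s*(TAU), because *q* cancels. With *s*(TAU) = 50%:

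| *q*, all arms | Overdoses per arm | SAEs, TAU | Texting, *s* = 50% | Texting, *s* = 40% | Texting, *s* = 25% |
|---|---|---|---|---|---|
| 10% | 8.4 | 4.2 | 4.2 | 3.4 | 2.1 |
| 20% | 16.8 | 8.4 | 8.4 | 6.7 | 4.2 |
| 30% | 25.2 | 12.6 | 12.6 | 10.1 | 6.3 |
| SAE ratio | – | – | 1.0 | 0.8 | 0.5 |

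Under the broad reading both arms have the count in the second column, and the ratio is 1.0 throughout.

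**4. Can a rise be hidden?** Take *q* = 20% in TAU and 25% in a texting arm, with *s*(TAU) = 50%, on the narrow reading. TAU has 84 × 0.20 × 0.50 = 8.4 SAEs. The texting arm has:
- *s* = 50%: 84 × 0.25 × 0.50 = 10.5, so the rise shows in full
- *s* = 40%: 84 × 0.25 × 0.40 = 8.4, so the rise disappears
- *s* = 25%: 84 × 0.25 × 0.25 = 5.25, so the direction reverses

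**5. Precision.** For the table's unequal-share contrasts, pairwise two-proportion power (two-sided 0.05) is about 5% to 34%. Any such SAE difference would be imprecise.

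Counting all overdoses helps, within limits. A doubling from 20% to 40% has power of about 0.81 at 84 per arm. If half are admitted in each arm, the hospitalized contrast of 10% versus 20% has about 0.44. Projected attrition rates gives 153 retained at month 12, or 153 / 3 = 51 per arm, where power for 20% versus 40% is about 0.60.

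At 20% in both arms, the 95% half-width for a difference is 1.96 × √(2 × 0.20 × 0.80 / *n*): about 12 percentage points for *n* = 84 and about 16 for *n* = 51.

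**The case against.** A reader might infer more: that the naloxone texts will make arms 1 and 2 look safer than they are. The documents do not support that.

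- **It depends on the narrow reading.** The protocol adopts the FDA definition and gives hospitalized and fatal overdose only as examples. If reversed overdoses are recorded as SAEs and reporting is complete, the distortion is nil. This stands, and it makes the effect conditional.
- **The arms differ in intensity only.** Harm-reduction pamphlets go to everyone approached (Vulnerable Subjects), and the OBOT programs provide naloxone whatever the arm. This stands; the texts add to a shared background.
- **The direction is not fixed.** Peer coaches contact arm 1 three times a week, which could raise detection of events and make that arm look less safe. This stands, and it is a further reason not to rely on the SAE count alone.
- **Fewer admissions or deaths would be a real benefit.** This also stands. An SAE difference of that kind is not spurious; it simply does not measure overdose frequency.
- **Survey data will be reviewed quarterly for harm, and the DSMB sees study data.** This helps, but neither passage names overdose or a comparison by arm.
- **The pause decision is not a count rule.** It requires SAE differences judged related to study procedures. So the plan cannot be said to pause, or fail to pause, mechanically on a distorted count.

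The omission itself is untouched: under either SAE reading, overdose is collected and no by-arm analysis is planned.

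**Conclusion.** The point holds in a limited form. Overdose has no planned by-arm analysis, the only stated between-arm safety comparison is of SAEs, and the protocol leaves open whether a reversed, non-admitted overdose enters that count. The SAE comparison may therefore not reflect overdose frequency.

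The documents do not fix the size or direction of any distortion. On the narrow reading, with an assumed share of 50% in TAU and 25% to 50% in a texting arm, the SAE ratio at equal overdose risk is 0.50 to 1.0. On the broad reading with complete reporting it is 1.0. Masking of a true rise is possible but depends on the assumed shares: a 25% relative increase vanishes at a 40% share and is fully visible at 50%.

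This does not affect the primary analysis. It is a gap in safety reporting that should be closed because the data are already being collected.

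**What to change.** 1. In Interim Data Analysis Plans and in the secondary and exploratory analyses of Aim 1, add a descriptive by-arm overdose table for each DSMB meeting and for the final report. Show the number and percentage of participants with at least one overdose, fatal or non-fatal and hospitalized or not, and episodes per person-time.
2. In the final report, give a 95% CI for each between-arm difference. No regression model is needed at DSMB meetings.
3. Show survey missingness by arm beside the table. Take fatal overdoses from SAE and discontinuation records, since a participant survey cannot report them.
4. Keep the all-SAE table, and split overdose SAEs into hospitalized, fatal and other.
5. Reconcile the SAE examples with the SAE definition so that the classification of a reversed, non-admitted overdose is stated and applied identically in all arms. Which classification to adopt is for the investigators and the DSMB.

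The cost is protocol and DSM-report wording plus one or two tables, with no new visits or instruments. The limitations are that non-fatal overdose is self-reported and that intervals will be wide, with about 51 per arm projected at month 12. The table should be read as description, not as a test of safety.
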